9 INTRODUCTION

9.1 Background

The investigational product – omadacycline (formerly named PTK 0796) – is the first member of the aminomethylcycline class of antibiotics, which are semi synthetic derivatives of the tetracycline class. As a class, the tetracyclines have been in use for approximately 70 years. They are well-tolerated, and have proven effective in the treatment of a variety of bacterial infections. Omadacycline is being developed for clinical use by both intravenous (iv) and per oral (po) administration. The targeted indications encompass community-acquired bacterial pneumonia (CABP), acute bacterial skin and skin structure infections (ABSSSI), and urinary tract infection (UTI).

When first approved, the tetracyclines were an important component of the antibiotic armamentarium. Their clinical use declined in subsequent years, due to the increasing prevalence of tetracycline resistance and the availability of effective alternative therapies.

Over the past decade, Gram-positive bacteria with multi-drug resistance to a diverse range of antibiotics have emerged as a major treatment challenge. Two developments raise the specter that currently available antibiotics may become even less useful for treatment of infections caused by Gram-positive organisms. The first is the emergence of vancomycin resistance in *Enterococcus* species (spp.) and the subsequent transfer of those resistance elements to *Staphylococcus aureus*. Although vancomycin-resistant *Staphylococcus aureus* have not become epidemiologically significant, their very existence raises concern because vancomycin has been the agent of choice for infections caused by resistant Gram-positive pathogens.

The second important development is the appearance of community-acquired methicillin-resistant *Staphylococcus aureus* (MRSA).¹ These strains are increasingly becoming multi-drug resistant over time. In many areas of the world, MRSA infections represent the majority of sporadic staphylococcal infections with community-onset. These strains also have been associated with numerous outbreaks of localized (skin and skin structure) and invasive (bacteremic) infections.

Omadacycline is very active *in vitro* against most Gram-positive pathogens. It also exhibits activity against atypical pathogens (eg, *Legionella* spp.), and some anaerobic and Gram-negative pathogens. The drug is active against strains expressing both mechanisms of tetracycline resistance as well as strains that are resistant to currently available antibiotics, including methicillin, vancomycin, erythromycin, and ciprofloxacin.²

Omadacycline has been developed for both iv and po administration and to date over 700 subjects have received one or both formulations in clinical studies. Across the completed Phase 1 studies, more than 500 subjects were exposed to omadacycline.

Single iv doses up to 600 mg and single po doses up to 600 mg have been investigated. Multiple iv doses of 100 mg once daily and 200 mg once daily for up to 14 and 7 consecutive days, respectively, have been investigated. Multiple po doses of 200 mg once daily and 300 mg once daily for up to 10 consecutive days have also been investigated. In a Phase 2 study, 219 subjects

with complicated skin and skin structure infections (cSSSI) were treated with omadacycline (n = 111) or linezolid (n = 108); treatment was initiated with iv administration, with switch to po therapy at the discretion of the investigator. In this study the total duration of study treatment was a mean of 10 and maximum of 20 days. In a sponsor terminated Phase 3 study of similar design, 140 subjects with cSSSI were treated with omadacycline (n = 68) or linezolid (n = 72) for a mean of 10 and maximum of 20 days for omadacycline and 22 days for linezolid.

In Phase 1 studies of iv administration, modest and reversible alanine aminotransferase (ALT) increases were seen, most notably with iv doses of 300 mg or greater. Transient increases in heart rate (HR) were observed following administration of single and multiple doses of omadacycline, with a dose dependent mean increase of up to 15 to 20 beats per minute (bpm) compared to placebo. The increases in HR were rarely reported as adverse events (AEs) and not associated with any other cardiac findings. These increases were most evident within the 6 hours post-infusion. Following po administration, an increased incidence of gastrointestinal (GI) AEs, particularly nausea, was noted in early studies, which were most notable at po doses of 400 mg or greater. Of note, different po formulations evaluated in early studies (eg, capsule versus tablet) may have influenced the GI safety profile. In Phase 1 studies there were no discontinuations due to drug-related AEs in any subject who received multiple doses of omadacycline.

In the Phase 2 cSSSI study, the most frequently reported AEs were GI related occurring in 19% of omadacycline treated and 17% of linezolid-treated subjects. Nausea and vomiting were reported in 10% and 5%, respectively, of omadacycline-treated subjects primarily during po treatment, compared to 7 and 4%, respectively, of linezolid-treated subjects. Premature discontinuation of treatment due to an AE was very infrequent, occurring in 0.9% of omadacycline subjects and 1.9% of linezolid subjects. There was no pattern of adverse changes in laboratory safety parameters among subjects treated with omadacycline or linezolid. In particular, there was no clinical or statistical difference between the treatment groups in ALT values or in other liver enzymes.

An increase in mean HR was observed, but to a lesser extent than what was observed in Phase 1 studies. This effect was transient and no QT prolongation was observed, consistent with the negative findings from testing of omadacycline in a dedicated corrected QT interval (QTc) study. Three subjects treated with omadacycline had AEs of tachycardia; 1 other subject reported palpitations. All 4 of these AEs were mild in intensity, all were assessed as either unrelated or unlikely related to test article, and none resulted in discontinuation of study treatment.

In the sponsor-terminated Phase 3 cSSSI study, 140 subjects were treated prior to the sponsor's decision to discontinue the study (due to changing regulations regarding the endpoints). The overall incidence of reported AEs in this study was comparable between the 2 treatment groups. The most commonly reported AEs (greater than or equal to 10% frequency in either treatment group) were nausea (27% omadacycline, 26% linezolid), headache (24% omadacycline, 7% linezolid), vomiting (9% omadacycline, 15% linezolid), diarrhea (4% omadacycline, 18% linezolid), and dizziness (10% omadacycline, 8% linezolid). Creatine phosphokinase (CK) elevation was reported in 9% of omadacycline treated subjects compared to 3% for linezolid. Alanine Aminotransferase increases were reported as AEs in 1 omadacycline subject (2%)

compared to 4 linezolid treated subjects (6%). Rash was reported by 1 omadacycline subject (2%) and 6 linezolid subjects (8%). Serious adverse events (SAEs) were experienced by 3 omadacycline subjects (small bowel obstruction, large left pleural effusion, and worsening depression) and 1 linezolid subject (worsening right hand cellulitis).

In a completed Phase 3 study comparing omadacycline and linezolid for the treatment of adults with ABSSSI (PTK0796-ABSI-1108), subjects started therapy with omadacycline 100 mg iv every 12 hours (q12h) for 2 doses then 100 mg iv every 24 hours (q24h), or linezolid 600 mg iv q12h. Subjects could be switched to oral therapy (omadacycline 300 mg q24h or linezolid 600 mg q12h) after a minimum of 3 days of iv therapy; the total treatment duration was 7-14 days. Study results showed that omadacycline was non-inferior to linezolid. In the modified intent-to-treat population (mITT, total N=627) for omadacycline versus linezolid, respectively, clinical success based on a reduction of lesion size at 48-72 hours after the first dose was 84.8% versus 85.5% (95% confidence interval [CI]: -6.3, 4.9); clinical success based on investigator's assessment of clinical response at 7-14 days after the last dose was 86.1% versus 83.6% (CI: -3.2, 8.2). Omadacycline was well tolerated: treatment-emergent adverse events (TEAEs) were reported in 48.3% versus 45.7%; serious TEAEs in 3.4% versus 2.5% and discontinuation due to TEAE in 1.9% versus 2.2% of omadacycline and linezolid treated subjects, respectively.

In addition, a global Phase 3 study is currently being conducted to evaluate the safety and efficacy of iv and po omadacycline compared to iv and po moxifloxacin in the treatment of adult subjects with community-acquired bacterial pneumonia (PTK0796-CABP-1200).

Please refer to the current version of the omadacycline Investigator's Brochure for additional information.²

Omadacycline has demonstrated activity against the most common ABSSSI pathogens, including isolates resistant to standards of care. This study is intended to evaluate the safety and efficacy of po omadacycline as compared to po linezolid in the treatment of adult subjects with ABSSSI.

10 STUDY OBJECTIVES

10.1 Primary Objectives

To demonstrate that omadacycline administered orally for 7 to 14 days is non-inferior to linezolid administered orally for 7 to 14 days in the treatment of adult subjects with ABSSSI known or suspected to be due to Gram-positive pathogens.

10.2 Secondary Objectives

- To evaluate the safety of omadacycline in the treatment of adult subjects with ABSSSI.
- To evaluate the Clinical Response according to the identified causative pathogen.
- To evaluate the pharmacokinetics (PK) of omadacycline in adult subjects with ABSSSI.

11 STUDY DESIGN

11.1 Description

This is a randomized (1:1), double-blind, double-dummy, active comparator-controlled, Phase 3 study comparing omadacycline and linezolid for the treatment of adult subjects with ABSSSI that is known or suspected to be due to a Gram-positive pathogen(s). Enrollment of subjects with major abscess may be up to 30% of randomized subjects. Enrollment of subjects who have received a single dose of an allowed short-acting antibiotic (see [Appendix 1](#)) within the 72 hours prior to randomization will be limited to no more than 25% of randomized subjects. Subject randomization will be stratified across treatment groups by type of infection (wound infection, cellulitis/erysipelas or major abscess) and receipt of an allowed antibacterial therapy (see [Appendix 1](#)) in the 72 hours prior to randomization, as defined in the Interactive Voice Response System/Interactive Web Response System (IxRS) specifications and statistical analysis plan (SAP) (see [Section 25.1](#)).

The study will consist of 3 protocol-defined phases: Screening, Double-Blind Treatment and Follow-up. All Screening evaluations, with the exception of the blood culture, should be completed within the 24 hours prior to randomization. The blood culture should be completed within the 24 hours prior to the first dose of test article. Subjects who meet inclusion criteria, and do not meet exclusion criteria will be randomly assigned to a treatment group, and should receive their first dose of test article at the site within 4 hours after randomization.

11.2 Rationale of Study Design

The study was designed in accordance with the United States (US) Food and Drug Administration (FDA)³ and European Medicines Agency (EMA)^{4,5} guidance on developing antimicrobial drugs for the treatment of ABSSSI, in addition to the guidelines of the Infectious Diseases Society of America (IDSA)⁶ and 2012 Update from the Biomarkers Consortium of the Foundation for the National Institutes of Health.⁷

11.3 Rationale for Choice of Comparator

The comparator drug, linezolid, is approved world-wide for the treatment of ABSSSI caused by Gram-positive pathogens and has an acceptable and well-defined safety profile. Linezolid can be administered orally and has regulatory approval for the treatment of ABSSSI caused by Gram-positive pathogens including MRSA.

11.4 Approximate Duration of Subject Participation

Subjects will participate in the study for approximately 30 days. Following Screening, eligible subjects will be randomly assigned to receive 7 to 14 days of po treatment with either omadacycline or linezolid. A follow-up office visit will occur approximately 7 to 14 days after the last dose of test article, and a follow-up telephone contact will occur approximately 30 to 37 days after the first dose of test article.

11.5 Approximate Duration of Study

This study is expected to be clinically complete in approximately 12 months.

11.6 Approximate Number of Subjects

Approximately 704 subjects will participate in this study at approximately 50 sites.

12 SELECTION OF SUBJECTS

Each subject must participate in the informed consent process and sign and date an institutional review board (IRB)/independent ethics committee (IEC)/research ethics board (REB) approved informed consent form (ICF) before any procedures specified in this protocol are performed.

12.1 Inclusion Criteria

To be eligible for randomization in this study, a subject must fulfill ALL of the following criteria:

1. Written and signed informed consent must be obtained before any assessment is performed.
2. Male or Female, age 18 years or older.
3. Has a qualifying skin and skin structure infection. All qualifying lesions must be greater than or equal to 75 cm² in total surface area of contiguous involved tissue, calculated as the product of the maximum length (head-to-toe) multiplied by the maximum width (measured perpendicular to length) as measured by the investigator using a wound ruler. Involved tissue is defined as tissue exhibiting clear evidence of one or more of the following: erythema, edema or induration.

The classification of qualifying infections is shown below.

- Wound infection – an infection characterized by purulent drainage from a wound with surrounding erythema, edema, and/or induration extending at least 5 cm in the shortest distance from the peripheral margin of the wound.
 - Cellulitis/erysipelas – a diffuse skin infection characterized by spreading areas of erythema, edema, and/or induration.
 - Major abscess – an infection characterized by a collection of pus within the dermis or deeper with surrounding erythema, edema, and/or induration extending at least 5 cm in the shortest distance from the peripheral margin of the abscess.
4. Has evidence of a systemic inflammatory response within the 24 hours prior to randomization, as indicated by ONE of the following:
 - Elevated white blood cell (WBC) count (greater than or equal to 10,000 cells/mm³) or leukopenia (less than or equal to 4,000 cells/mm³)
 - Elevated immature neutrophils (greater than or equal to 15% band forms, see % bands calculation in [Appendix 2](#)) regardless of total peripheral WBC count
 - Lymphatic involvement: lymphangitis or lymphadenopathy that is proximal to and in a location that suggests drainage from the qualifying infection

- Fever or hypothermia documented by the investigator (temperature greater than 38.0°C [100.4°F] or less than 36.0°C [95.5°F])
5. Females must have a negative pregnancy test at Screening and agree to comply with using an acceptable method of birth control (eg, abstinence, oral contraceptive, intrauterine device [IUD], barrier contraception [condom], tubal ligation, hysterectomy, bilateral oophorectomy, postmenopausal or vasectomized partner) from Screening through Post Therapy Evaluation (PTE). Males must agree to use an acceptable method of birth control with female partner(s) and must not donate sperm from Screening through PTE.

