16.1.1 Vital Signs

Vital signs include BP, pulse/heart rate, body temperature, and respiratory rate. Vital signs should be recorded at all visits, with the exception of the Final Follow-up assessment (see [Section 8](#)).

- In addition, blood pressure and pulse rate should be measured within 30 min before, and approximately (\pm 15 minutes) 1 hour after and 3 hours after the completion of the first dose on Day 1
- Blood pressure and pulse rate should be measured within 30 min before, and approximately (\pm 15 minutes) 1 hour after and 3 hours after the completion of the odd numbered dose on Day 2
- Blood pressure and pulse rate should be measured within 30 min before, and approximately (\pm 15 minutes) 1 hour after and 3 hours after the completion of the odd numbered dose on Day 3

In the event that the subject takes the dose before arriving for the Day 2 or Day 3 office visit, the site should collect the 1 and 3 hour post dose measurements if possible, if not then a single measurement should be made at any time during the visit and the date and time recorded.

The subject's vital signs should be captured after at least 5 minutes of rest while in a non-standing position (supine or semi-recumbent, head of bed from 0° to 90°). Subsequent vital sign measurements should be captured in the same non-standing position.

Systolic and diastolic blood pressure will be measured using an automated validated device, with an appropriately sized cuff.

Pulse will be measured using an automated validated device, when available. If not available, pulse will be measured manually.

In addition to the above, BP and heart rate may be measured whenever clinically indicated at the discretion of the treating physician. Any subject who experiences an AE of cardiac chest pain, palpitations, or tachyarrhythmia while on study should have an ECG and an evaluation by the investigator (see [Section 16.1.3.1](#)).

Temperature will be obtained using an electronic (rapid reading) device whenever possible. Respiratory rate will be determined by observation.

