Appendix 2. Equations and Conversion Factors

1. Cockcroft-Gault equation to calculate creatinine clearance (CrCL) (relevant to Exclusion Criterion number 8):

$$\frac{(140 - \text{age}[\text{yrs}]) * \text{weight} [\text{kg}] * (Z)}{\text{Cr} [\text{mg/dL}] * 72}$$

Z = 1.0, if Male
Z = 0.85, if Female

2. $\text{mm}^3 = \mu\text{L}$
3. $\text{cc} = \text{mL}$
4. Conversion of immature neutrophils (band) forms in K/ μL or K/mL to % bands (relevant to Inclusion Criterion number 4 and Exclusion Criterion number 11):
[(bands K/ μL)/(total WBC K/ μL)] \times 100 = % bands
Or
[(bands K/mL)/(total WBC K/mL)] \times 100 = % bands

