6.1.3 Modified Intent-to-Treat (mITT) Population

The mITT population will consist of all randomized subjects without a baseline sole Gram-negative ABSSSI pathogen. Pathogen determination is described in Section 6.1.4.

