6.1.5.1 Diagnosis of ABSSI

To be included in the CE-EOT and CE-PTE populations, subjects must meet the following protocol defined inclusion criteria that describe the ABSSI:

Inclusion Criterion 3: Has a qualifying skin and skin structure infection. All qualifying lesions must be greater than or equal to 75 cm² in total surface area of contiguous involved tissue, calculated as the product of the maximum length (head-to-toe) multiplied by the maximum width (measured perpendicular to length) as measured by the investigator using a wound ruler. Involved tissue is defined as tissue exhibiting clear evidence of one or more of the following: erythema, edema, or induration.

The classification of qualifying infections is shown below:

- a. Wound infection – an infection characterized by purulent drainage from a wound with surrounding erythema, edema, and/or induration extending at least 5 cm in the shortest distance from the peripheral margin of the wound.
- b. Cellulitis/erysipelas – a diffuse skin infection characterized by spreading areas of erythema, edema, and/or induration.
- c. Major abscess – an infection characterized by a collection of pus within the dermis or deeper that is accompanied by erythema, edema and/or induration extending at least 5 cm of in the shortest distance from the peripheral margin of the abscess.

Inclusion Criterion 4: Has evidence of a systemic inflammatory response within the 24 hours prior to randomization, as indicated by ONE of the following:

- a. Elevated white blood cell (WBC) count (greater or equal to 10,000 cells/mm³) or leukopenia (less than or equal to 4,000 cells/mm³)
- b. Elevated immature neutrophils (greater than or equal to 15% band forms) regardless of total peripheral WBC count
- c. Lymphatic involvement: lymphangitis or lymphadenopathy that is proximal to and in a location that suggests drainage from the qualifying infection
- d. Fever or hypothermia documented by the investigator (temperature greater than 38.0°C [100.4°F] or less than 36.0°C [95.5°F])

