6.2.2 Process for Determining Inclusion in Populations

Inclusion into the ITT and Safety populations will be determined programmatically from the eCRF data. Inclusion into the CE populations will be determined programmatically from the

eCRF data and the manual review conducted by the ERT. The ERT may review subject data to confirm that population criteria are satisfied.

Inclusion into the mITT and micro-mITT population will be determined programmatically by incorporating the outcome of the review of the isolates by the ERT. The ERT will determine whether each isolate (baseline and post-baseline) is considered a pathogen based on a review of information from baseline samples including infection type, type of specimen, and local and central laboratory genus and species identification. Inclusion into the ME populations will be determined programmatically.

Review of data, Sponsor determination of evaluability, and final subject population classification will be performed in a blinded manner prior to database lock and unblinding with the exception of those criteria requiring the subject's actual treatment assignment (for example, the requirement for the subject to have received the correct test article per the randomization assignment). For the criteria requiring the subject's actual treatment assignment, population determination will be completed programmatically after unblinding.

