6.3 Subgroups

Analyses of Early Clinical Response and the overall assessment of Clinical Response at the PTE Visit (based on the investigator's assessment) will be conducted (as described in [Section 10.6](#)) for subgroups defined by the randomization stratification factors: infection type (cellulitis/erysipelas, wound infection and major abscess) and receipt of an allowed antibacterial therapy in the 72 hours prior to randomization (yes or no). Analyses of Early Clinical Response will also be conducted in the following subgroups: clinical site (sites that enroll less than 10 subjects per group will be grouped together), bacteremic subjects, subjects meeting the systemic inflammatory response syndrome (SIRS) criteria at baseline, size of lesion ($\leq 300 \text{ cm}^2$, > 300 to 600 cm^2 , > 600 to 1000 cm^2 , and $> 1000 \text{ cm}^2$), receipt of a nonsteroidal anti-inflammatory drug (NSAID) from the first dose of test article through to the assessment of Early Clinical Response, receipt of an operative incision and drainage (I&D) from the first dose of test article through to the assessment of Early Clinical Response and IV drug use vs no IV drug use. SIRS is defined as having 2 or more of the following criteria: temperature $< 36^\circ \text{ C}$ or $> 38^\circ \text{ C}$, heart rate > 90 bpm, respiratory rate > 20 bpm, or WBC count $< 4000 \text{ cells/mm}^3$ or $> 12,000 \text{ cells/mm}^3$ or $> 10\%$ bands.

Exploratory analyses in other subgroups may also be conducted.

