Listings will be provided of those subjects who were randomized to the wrong ABSSSI type of infection stratum and wrong prior antibiotic stratum. The type of infection listing will provide the subject ID, treatment group, randomized type of infection and actual (as recorded on the eCRF) type of infection. The prior antibiotic listing will provide the subject ID, treatment group, randomization date and time, randomized prior antibiotic stratum, preferred term of prior antibiotic, start and stop date/time of prior antibiotic, hours prior to randomization, dose and frequency of the antibiotic.

Descriptive statistics of the primary infection site will be provided for the mITT and CE-PTE populations. These include type of ABSSSI infection (cellulitis/erysipelas, major abscess, wound infection) and anatomical site (categorized as scalp, neck, face, chest, abdomen, back, groin, hand, foot, shoulder, buttock, axillary, arm, leg, elbow and knee). Lesion measurements (length, width and area of erythema, edema and/or induration, and for subjects with wounds and abscesses, the shortest measurement from peripheral margin), local signs and symptoms (tenderness, edema, erythema, induration, and drainage [none, serous/serosanguineous, seropurulent, and purulent]), and systemic signs (lymphadenopathy proximal to primary lesion site, presence of lymphangitis proximal to primary lesion site, WBC count $\geq 10,000$ cells/mm³ or ≤ 4000 cells/mm³, $\geq 15\%$ immature neutrophils, temperature [as a continuous variable and defined as fever/no fever at baseline $> 38.0^{\circ}\text{C}$, hypothermia $< 36.0^{\circ}\text{C}$]) will be summarized by treatment group. The percentage of subjects meeting the systemic inflammatory response syndrome (SIRS) criteria at baseline will also be provided (yes vs no). SIRS is defined as having 2 or more of the following criteria: temperature $< 36^{\circ}\text{C}$ or $> 38^{\circ}\text{C}$, heart rate > 90 bpm, respiratory rate > 20 bpm, or WBC count < 4000 cells/mm³ or $> 12,000$ cells/mm³ or $> 10\%$ bands. Descriptive statistics of baseline lesion area and a summary of the local signs and symptoms will also be provided by treatment group separately by type of ABSSSI infection (actual as recorded on the eCRF). Differences between treatment groups will be analyzed using Fisher's exact test for dichotomous variables and the Wilcoxon Rank Sum test for ordinal and continuous variables.

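### The hypothermia limit is printed as two different temperatures (36.0°C is 96.8°F, not 95.5°F), and neither document says which one governs entry and the CE check

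*Protocol*

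**What the plan says.** Inclusion criterion 4 in Protocol 12.1 requires one of four systemic signs within 24 hours before randomization. The temperature sign is written "temperature greater than 38.0°C [100.4°F] or less than 36.0°C [95.5°F". The same pair of limits is printed in five places:

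- Synopsis, inclusion criterion 4
- Synopsis, exclusion criterion 11 (septic shock)
- Protocol 12.1, inclusion criterion 4
- Protocol 12.2, exclusion criterion 11
- SAP 6.1.5.1, which restates inclusion criterion 4 as a condition of CE membership: "To be included in the CE-EOT and CE-PTE populations, subjects must meet the following protocol defined inclusion criteria"

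Other passages touch on temperature or on how the limit is applied:

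- Protocol 16.1.1 covers the measurement but names no unit: "Temperature will be obtained using an electronic (rapid reading) device whenever possible".
- Protocol Appendix 2 gives a percent-bands conversion for "Inclusion Criterion number 4 and Exclusion Criterion number 11", but no temperature conversion.
- SAP 6.3 ("SIRS is defined as having 2 or more of the following criteria: temperature" and so on) and the baseline systemic signs in SAP 9.2 ("as a continuous variable and defined as fever/no fever at baseline") give their temperature limits in Celsius only, with the low limit at 36°C.
- SAP 6.2.2 says how CE status is set: "Inclusion into the CE populations will be determined programmatically from the" eCRF data, together with manual review by the blinded Evaluability Review Team.

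**The concern.** The Fahrenheit figure stands inside an operative entry criterion, and it is a different temperature from the Celsius figure beside it. A site with a Fahrenheit thermometer would naturally apply the printed 95.5°F. The limits are nested: anyone below 95.5°F is also below 36.0°C. A site reading Fahrenheit therefore applies the stricter entry rule, and since one sign suffices, temperature alone can decide eligibility. About 50 sites are planned, so one protocol could be run with two entry rules.

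The second exposure is in the analysis populations. SAP 6.1.5.1 makes inclusion criterion 4 a condition of CE-EOT and CE-PTE, and the ME populations are drawn from those. A programmer must choose one number where the SAP prints two. The same choice decides whether a subject appears in the SAP 9.1 listing of unmet criteria and in the SAP 13.1 deviation category for an unmet inclusion criterion. Under the EMA analysis in Protocol 22.4.3, non-inferiority at PTE must be shown in CE as well as mITT, so CE membership is not merely descriptive there.

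**Working it through.** **Conversion.** °F = °C × 1.8 + 32, and °C = (°F − 32) / 1.8.

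| Printed limit | Check | Result |
|---|---|---|
| Fever, 38.0°C [100.4°F] | 38.0 × 1.8 + 32 | 100.4°F, agrees |
| Hypothermia, 36.0°C | 36.0 × 1.8 + 32 | 96.8°F, printed as 95.5°F |
| Hypothermia, 95.5°F | (95.5 − 32) / 1.8 | 35.28°C, printed as 36.0°C |

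The gap is 96.8 − 95.5 = 1.3°F, or 36.0 − 35.28 = 0.72°C. Rounding does not explain it: 35.95 to 36.05°C covers 96.71 to 96.89°F, and 95.45 to 95.55°F covers 35.25 to 35.31°C.

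**Who is affected.** Readings from 95.5°F up to but not including 96.8°F (35.28 to <36.0°C) meet the Celsius limit and fail the Fahrenheit one. For example, 96.0°F is (96.0 − 32) / 1.8 = 35.56°C. Entry changes only if such a subject has no qualifying white cell count, band count or lymphatic sign. For exclusion criterion 11 the reach is very narrow, because its septic shock definition needs all six components.

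**Which populations use the limit.** SAP 6.1.3 reads "The mITT population will consist of all randomized subjects without a baseline sole Gram-negative ABSSSI pathogen", so mITT membership among randomized subjects does not depend on it. CE-EOT and CE-PTE do, and ME follows from CE:

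- If 36.0°C is programmed, nobody loses CE status through this discrepancy.
- If 95.5°F is programmed, a subject enrolled on a temperature in the band with no other sign leaves CE.

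**Effect on CE power.** Inputs from Protocol 22.13: margin 10%, 1-sided alpha 0.025, equal rates in both arms, 1:1 allocation. With n per arm, Farrington–Manning power is Φ[(0.10·√n − 1.96·s₀) / s₁]. Here s₁² = 2p(1 − p), and s₀² is the sum of the two binomial variances at the rates fitted under a difference of −10%.

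First, the plan's own table:

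| Outcome rate | Total N | Power recomputed | Power printed |
|---|---|---|---|
| 79% | 704 | 90.0% | 90% |
| 85% | 704 | 95.6% | 96% |
| 90% | 564 | 96.9% | 97% |

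For the CE line, n = 282. The fitted rates are 0.831 and 0.931, so s₀ = 0.4519 and s₁ = 0.4243. Then (0.10 × 16.793 − 1.96 × 0.4519) / 0.4243 = 1.87, and Φ(1.87) = 0.969.

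The documents do not say how many subjects would qualify only on a temperature in the band. The losses below are assumptions, and they apply only if 95.5°F is programmed:

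| Assumed loss from CE | CE N | Power at 90% |
|---|---|---|
| none | 564 | 96.9% |
| 1% | 564 × 0.99 ≈ 558 | 96.8% |
| 2% | 564 × 0.98 ≈ 553 | 96.7% |
| 5% | 564 × 0.95 ≈ 536 | 96.2% |

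**The case against.** The best defence is that this is a wrong bracketed equivalent rather than two competing thresholds. Celsius comes first in all five places. Outside the copied criterion, every temperature limit in the SAP is in Celsius alone, and SAP 9.2 lists nearly the same systemic signs as inclusion criterion 4 with hypothermia at <36.0°C. No passage uses 95.5°F on its own. That is fair evidence of what was intended, but it is indirect: SAP 6.3 and 9.2 define a subgroup and baseline tables, not entry or the CE check. A site deciding eligibility works from the protocol criterion.

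It can also be said that the CE loss is hypothetical, since it needs 95.5°F to be programmed, and that the Evaluability Review Team reviews CE status blinded. The criterion is applied before randomization in a double-blind trial, so the entry discrepancy itself does not favour an arm. In this FDA SAP the CE comparison at PTE is descriptive (SAP 10.3). All of this stands. It limits the consequences but does not remove the contradiction from the entry criterion and the CE rule.

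**Conclusion.** The concern holds. The hypothermia limit is stated as two temperatures 1.3°F (0.72°C) apart, in five places across both documents, and nothing in either document says which one governs entry or CE membership. The conversion is certain and rests on no assumption.

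The practical effect is probably small, and the number of subjects cannot be derived from the documents. It needs a reading in a narrow band, no other qualifying sign, and use of the Fahrenheit figure by a site or programmer. The harm is inconsistent eligibility and deviation classification, not lost power: even an assumed 5% loss from CE leaves 96.2%. The sample size and the planned power for Early Clinical Response do not use the limit, and the mITT set changes only through who is randomized. The point should be fixed because it sits in an operative criterion and the correction is cheap.

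**What to change.** Reconcile the Celsius and Fahrenheit figures in all five places (synopsis inclusion 4 and exclusion 11, Protocol 12.1 and 12.2, SAP 6.1.5.1) so that both units state one threshold, consistent with the Celsius-only definitions in SAP 6.3 and 9.2. Notify sites of the reconciled figure. Program that single threshold for CE membership and for the eligibility-deviation checks before database lock.

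The cost is a text correction in five places, a note to sites and one programmed value. Sample size, the mITT definition and the primary analysis stay as they are.
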